Individuals will be excluded if they are unable to provide informed consent, report contraindications for CBT-I (mania or seizure disorder), work on a rotating shift schedule, have a severe or untreated psychiatric disorder that requires immediate clinical attention (e.g., psychosis, suicidal ideation with intent and plan), or are already receiving behavioral treatment for insomnia.

6. Drugs/ Substances/ Devices

N/A

7a. Primary Outcomes

Recruitment. Completion of 1+ session of CBT-I will be used to indicate recruitment.

Retention. Completion of all sessions of CBT-I will be used to indicate retention.

Client Satisfaction Questionnaire. The Client Satisfaction Questionnaire (Larsen, Attkisson, Hargreaves, & Nguyen, 1979) is an 8-item measure of satisfaction with treatment that has been validated in substance use treatment settings (Kelly et al., 2018). Items are scores from 1 to 4, with higher scores indicating greater satisfaction with treatment. For example, response options for the item, “How would you rate the quality of services you received?” range from 1 (poor) to 4 (excellent).

Timeline Followback. The Timeline Followback (TLFB) will be used as a face-valid measure of change in drinking quantity and frequency from baseline to follow-up (Sobell & Sobell, 1996). Using a calendar-based form, participants will indicate how many standard drinks they consumed on each day over the past 6 weeks. Holidays and significant historical events will be labeled to enhance memory recall. The TLFB will be used to estimate percentage of abstinent days and percentage of heavy-drinking days (4/5+ drinks for women/men).

Brief Young Adult Alcohol Consequences Questionnaire. The Brief Young Adult Alcohol Consequences Questionnaire (BYAACQ) is a 24-item measure of alcohol-related problems that has demonstrated reliability and concurrent validity among young adults who drink alcohol (Kahler, Hustad, Barnett, Strong, & Borsari, 2008; Kahler, Strong, & Read, 2005). Participants indicate (yes/no) if they have experienced consequences such as saying/doing embarrassing things, taking foolish risks, drinking on nights they had planned not to drink, or passing out from drinking in the past 30 days. Possible total scores range from 0 to 24.

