Insomnia Severity Index. The Insomnia Severity Index (Morin, Belleville, Belanger, & Ivers, 2011) will be used as a 7-item measure of insomnia severity in the past two weeks. Items assess difficulty falling or staying asleep, satisfaction with current sleep pattern, interference with daily functioning, the extent to which others notice their sleep problems, and worry/distress related to sleep problems. Response options range from 0 (not at all worried) to 4 (very much worried), with possible total scores ranging from 0 to 28. Participants scoring 10 or higher will be classified as screening positive for insomnia (Morin et al., 2011). Notably, self-report is the recommended method of assessment for symptoms of insomnia in adults (Schutte-Rodin et al., 2008).

Actiwatch 2. The Actiwatch 2 (Philips Respironics) is a watch-like device that monitors body movement. Actigraphy data will be used in conjunction with self-report data to estimate sleep onset latency, wake after sleep onset, and total sleep time. Data will be analyzed by proprietary software using 30s epochs. Actigraphy provides valid estimates of nighttime awakenings, wake after sleep onset, total sleep time, and sleep efficiency when compared to polysomnography (Kushida et al., 2001; Lichstein et al., 2006).

Daily Sleep Diary. The sleep diary used in this study includes all elements of the consensus sleep diary used in sleep studies across the nation (Carney et al., 2012). Participants will estimate what time they got into bed, what time they tried to go to sleep (bedtime), how long it took them to fall asleep (sleep onset latency), the total duration of nighttime awakenings (wake after sleep onset), the time of their final awakening (waketime), and what time they got out of bed for the day. Sleep onset latency and wake after sleep onset will be summed to

estimate total wake time. Total wake time will be subtracted from time in bed to estimate total sleep time. Participants will also rate sleep quality on a scale from 0 (very poor) to 4 (very good). Finally, they will be asked to report the number of standard drinks consumed; if they used alcohol (yes/no), marijuana (yes/no), or other illicit drugs (yes/no) to help with sleep; and the name, dose, and time of any sleep medication they used to help with sleep.

7b. Secondary Outcomes

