Behavior Rating Inventory of Executive Function for Adults (BRIEF-A). The BRIEF-A (Rabin et al., 2006) is a 75-item measure of executive function comprised of two index scores: the Behavioral Regulation index (BRI) and the Metacognitive Index (MI). In turn, the BRI is comprised of four subscales (inhibit, shift, emotional control, and self-monitor), and the MI is comprised of five subscales (initiate, working memory, plan/organize, task monitor, and organization). Consistent with the measure detailed on the Science of Behavior Change website and the theoretical model of executive function detailed in this proposal, we will use the initiate, working memory, plan/organize, and task monitor subscales of the MI index to assess self-reported executive function. Participants will indicate how often in the past month statements such as, “I make careless mistakes when completing work,” and, “I start work (such as cooking, projects) without the right tools,” have applied to them. Response options range from 1 (never a problem) to 7 (always a problem).

Monetary Choice Questionnaire. The Monetary Choice Questionnaire (Kirby, Petry, & Bickel, 1999) will be used as a self-report measure of delay discounting. In 27 trials, participants will be asked to choose between a smaller, immediate reward or a larger, delayed reward. For example, “Would you prefer \$54 today or \$55 in 117 days?” Data will be used to calculate participants’ discounting-rate parameter (k).

Positive and Negative Affect Schedule. Participants will indicate the extent to which they feel each of 20 mood states (10 positive and 10 negative) on a scale from 1 (*very slightly or not at all*) to 5 (*extremely*).

Difficulties in Emotion Regulation Scale. The 16-item Difficulties in Emotion Regulation Scale has demonstrated good convergent and discriminant validity in clinical and community samples (Bjureberg et al., 2015). On a scale from 1 (almost never) to 5 (almost always), participants will indicate how often in the past 6 weeks they would endorse items such as, “I have difficulty making sense out of my feelings,” and, “When I am upset, I become out of control.”

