Data analysis. All questionnaire and behavioral task data will be scored according to published conventions. We will test for group equivalence in gender, age, race/ethnicity, use of sleep medication (# LRD), use of other drugs, and perceptions of peer drinking quantities (descriptive norms) at baseline. Group differences are unexpected in the context of randomization; however, if one of these variables is associated with both group and a given outcome variable, we will include it as a covariate in the prediction of that outcome. Data will be screened for integrity, outliers, missing values, and violations of the assumptions of MLM. Outliers will be replaced with the value that is 3 standard deviations +1 unit above the mean (Tabachnick & Fidell, 2007), and missing values will be handled in MLM using full maximum likelihood estimation.

Cohen's *d* and 95% CIs will be used to examine the magnitude of between-group differences mid-treatment, post-treatment, and at 1-month follow-up. We chose MLM over other statistical approaches because it requires fewer assumptions and has superior ability to handle missing data. In each model, the Level 1 variable will be time. Level 2 portions of the model will include the effect of condition and necessary covariates. The impact of CBT-I on insomnia symptoms will be tested by regressing condition on the Level 1 intercept and time effect. We will examine whether attrition is associated with any baseline variables and control for such variables when necessary. We will also explore CBT-I effects on alcohol use and proposed mediators, though we will be underpowered to detect small to moderate effects. We will use MLM to examine the within-individual associations between insomnia symptoms and alcohol use.

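### The plan's only outlier rule gives one high-side replacement value, so followed as written it sends low outliers to the opposite tail and can carry a small-scale outcome past its maximum

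*Combined protocol and SAP*

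**What the plan says.** Outliers are dealt with only in the Data analysis paragraph of section 8 (Study Statistics). Detection is covered by a general statement: "Data will be screened for integrity, outliers, missing values, and violations of the assumptions of MLM". Replacement is covered by the next relevant sentence: "Outliers will be replaced with the value that is 3 standard deviations +1 unit above the mean", with a textbook citation.

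That sentence applies to outcomes on very different scales. In section 7a, "The TLFB will be used to estimate percentage of abstinent days and percentage of heavy-drinking days", so those are 0-100 quantities. The Insomnia Severity Index has "possible total scores ranging from 0 to 28", and diary sleep quality is rated 0 to 4. In section 7b, the Monetary Choice Questionnaire gives a discounting rate k, whose scale is not stated.

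The plan does not say what makes a value an outlier, what the unit is, or what replaces a low outlier. It does not say whether the mean and SD are taken overall, by arm or by visit, or whether a replacement is held within the scale. No analysis of unreplaced data is planned.

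**The concern.** A replacement rule of this kind should pull an extreme value towards the rest of the data on its own side. This one states a single value above the mean. For a low outlier, that value lies on the wrong side of the distribution.

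The low tail matters here. A participant with no abstinent days is a possible and informative case in an alcohol trial. Eligibility (section 5) can be met with one heavy-drinking episode or one alcohol-related consequence in 30 days, so a sample with a high average share of abstinent days, in which 0% stands out, is not ruled out.

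The added unit raises a second issue. On a scale with a small SD, one raw unit is large, so the replacement can lie further out than the value it replaces, or outside the scale. At stake are the arm means, and the SDs behind the planned Cohen's *d*, in a trial with 22 people per arm.

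**Working it through.** **From the plan:** the replacement rule and the outcome scales above; 44 participants in the final sample, 22 per arm (section 1).

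**Assumed, because the plan is silent:** all outcome means and SDs; a 3 SD cut-off; one outlier among 44 values at one visit; mean and SD computed over both arms with the outlier included; unit u = 1.0 raw unless stated.

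**The plan's own figure.** No figure is attached to the outlier rule. The sample size of 44 reproduces: λ = f²·N·m/(1 − ρ) = 0.0625 × 44 × 4/0.6 = 18.3, with 3 and 126 df, gives power 0.957. Nothing below alters it.

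**Formulas.** For 43 values with mean m and SD s, plus one outlier x:

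- mean M = (43m + x)/44
- SD² = [42s² + (43/44)(x − m)²]/43
- replacement R = M + 3 SD + u
- arm-mean shift = (R − x)/22

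**Low tail: 0% abstinent days (x = 0)**

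| Other 43 (mean/SD) | M / SD | z of 0% | R as written | Arm shift | M − 3 SD | Arm shift if M − 3 SD is used |
|---|---|---|---|---|---|---|
| 75/15 | 73.3/18.6 | −3.9 | 130.2% | +5.9 points (0.32 SD) | 17.4% | +0.8 (0.04 SD) |
| 80/12 | 78.2/16.9 | −4.6 | 129.9% | +5.9 points (0.35 SD) | 27.4% | +1.2 (0.07 SD) |
| 60/25 | 58.6/26.3 | −2.2 | not flagged | none | – | – |

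The unit hardly matters in this table: dropping it lowers R by 1 point and the arm shift by 1/22 = 0.05 point. What matters is the tail. Capping at 100% without changing the tail would still move the arm mean by 100/22 = 4.5 points.

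**High tail, u = 1.0**

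| Outcome, other 43 (mean/SD), outlier | SD of 44 | M + 3 SD | R | Arm shift in SD |
|---|---|---|---|---|
| Sleep quality 1.5/0.5, 3.6 | 0.587 | 3.31 | 4.31 (maximum 4) | +0.055 |
| Sleep quality 1.8/0.5, 3.8 | 0.579 | 3.58 | 4.58 (maximum 4) | +0.061 |
| Insomnia Severity Index 8/4, 24 | 4.63 | 22.26 | 23.26 | −0.007 |
| Heavy-drinking days 10/15, 80 | 18.2 | 66.2 | 67.2 | −0.03 |

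In general R lies at z = 3 + u/SD. With u = 1 that is 3.25 to 3.17 for SDs of 4 to 6, and 3.10 to 3.03 for SDs of 10 to 30, so the added unit is harmless on the larger scales. The largest z possible among 44 values is 43/√44 = 6.48. Below an SD of 1/(6.48 − 3) = 0.287, every high outlier beyond 3 SD would therefore move outward.

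**Raw k, u = 1.0.** With the others at 0.01/0.01 and an outlier of 0.06, R = 0.0111 + 3 × 0.0124 + 1 = 1.048. With otherwise equal arms of 22, the arm difference goes from 0.05/22 = 0.0023 to 1.038/22 = 0.0472. The pooled SD goes from 0.012 to 0.157, so *d* goes from 0.18 to 0.30. With the others at 0.05/0.05 and an outlier of 0.35, R = 1.258 and *d* goes from 0.20 to 0.29.

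**If the unit is instead the smallest step** (assumed 0.0001 for k, 1/14 for a 14-day diary mean), the same values move inward: 0.06 to 0.0485, 0.35 to 0.258, 3.6 to 3.38 and 3.8 to 3.65. The direction changes at u = x − (M + 3 SD): 0.012 and 0.092 for k, 0.29 and 0.22 for sleep quality.

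**The case against.** The strongest reply is that this is ordinary shorthand for a textbook rule. The source may define the unit and the cut-off, and no competent analyst would send 0% to 130%. That probably describes what would happen in practice. But the analyst would then be applying a low-tail rule that the plan does not contain, chosen after seeing which participants are affected. The plan's own wording has only a high-side value.

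Several other objections stand and limit the point:

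- The outward movement of high values depends on the unit being 1.0 raw, on a 3 SD cut-off and on assumed SDs. A reader might infer that the rule generally pushes outliers outward. The documents do not support that: they give no SD and leave the unit undefined, and on the larger scales the effect is negligible.
- For raw k, a reader might quote the arm-mean shift against the SD before replacement, 0.045/0.0124 = 3.6 SD. That overstates the effect on the planned measure. The replaced value also inflates the SD, so *d* moves by about 0.1; the inflated SD could mask a real difference. Nor does the plan say that k would be analysed untransformed.
- For sleep quality, the contrast between the two readings of the unit needs a step of 1/14. If ratings are whole numbers and the step is taken as 1, both readings give 4.31 and 4.58.
- Feasibility and acceptability are the first objective, and the recruitment and retention measures are untouched.

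**Conclusion.** The rule is wrong as written, and the point is minor. The one-sidedness is read directly from the text. The cut-off, the unit and all means and SDs behind the sizes are assumptions.

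The largest effect found on a primary outcome is in the low tail: about 5.9 points, or 0.32 to 0.35 SD, on an arm mean for abstinent days if the sentence is followed literally. It is 0.04 to 0.07 SD if the analyst moves the value to mean − 3 SD instead, and nothing in the assumed distribution where 0% is not flagged. High-side replacement moves the primary outcomes checked by about 0.06 SD or less, although it can produce impossible sleep-quality values. For raw k, a secondary outcome, the main effect is SD inflation.

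A reader might go further and infer that the trial's power or its main conclusions are compromised. The documents do not support that: no sample size or power figure depends on this rule, and the plan itself describes the alcohol and mediator analyses as exploratory.

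**What to change.** Rewrite the sentence before the data are analysed:

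- State the cut-off, and the mean and SD used: overall, by arm or by visit, and with or without the flagged value.
- Replace each outlier in its own tail, with mean + 3 SD or mean − 3 SD. The added unit could be kept if it is defined as each scale's smallest step and applied symmetrically.
- Cap every replacement at the limits of the scale. A cap alone is not enough, because it leaves low outliers in the wrong tail.
- Report one sensitivity analysis on unreplaced data, especially for the drinking outcomes, where extreme values may be genuine.

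The cost is a wording change, a few lines of code and one additional analysis. Sample size, visits and data collection stay the same.

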Cognitive Behavioral Therapy (CBT-I) is the first line of treatment for insomnia (Rybarczyk, Lund, Mack, & Stepanski, 2009; Schutte-Rodin, Broch, Buysse, Dorsey, & Sateia, 2008; Siebern & Manber, 2011). It has moderate to large effects among Veterans, with improvements documented up to 6 months (between-group effect sizes=0.5-0.8; 10-11% more time asleep in bed at post-treatment and 6mo) (Edinger et al., 2009; Germain et al., 2014; Karlin, Trockel, Taylor, Gimeno, & Manber, 2013; Taylor et al., 2018). Research with college students (Fucito et al., 2017; Hershner & O'Brien, 2016) and animal models (Vengeliene, Noori, & Spanagel, 2015) suggests that improvements in insomnia may reduce heavy alcohol use, and pharmacological treatment of insomnia has been found to delay relapse among individuals with alcohol use disorder (AUD) (Anton et al., 2011; Brower et al., 2008). Based on this research, **CBT-I is expected to reduce insomnia symptoms among heavy-drinking Veterans**, thereby resolving insomnia-related deficits in executive functioning, negative emotionality, and craving for alcohol, as well as use of alcohol as a sleep aid. **These improvements, in turn, are expected to reduce alcohol use and related problems.** This line of research is particularly promising for Veterans, as Veterans generally perceive stigma toward mental health treatment (Vogt et al., 2014) but indicate interest in treatment for insomnia (Hom et al., 2016; Plach & Sells, 2013; Shepardson, Funderburk, Pigeon, & Maisto, 2014).

4. Study Procedures

This research will examine the efficacy of CBT-I in improving sleep and alcohol use outcomes among heavy-drinking OEF/OIF/OND-era Veterans. Forty-four Veterans will be randomized to receive sleep hygiene or to participate in five sessions of individual Cognitive Behavioral Therapy for Insomnia (CBT-I). Outcomes will be assessed at baseline, mid-treatment (3 weeks), post-treatment, and 3-month follow-up (see Figure 1).

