As of April/May of 2022, BuildClinical will manage all digital marketing recruitment for this study. BuildClinical is a data-driven digital marketing company that helps academic researchers recruit participants for research studies more efficiently using social media, software, and machine learning. They will ensure that all IRB-approved guidelines and procedures are followed during recruitment. They use study-specific advertisements to engage participants on digital platforms such as Facebook, Google, WebMD, etc. Participants who click on the advertisements will be redirected to a study-specific landing page. On the landing page, the person can complete an online pre-screen questionnaire. Pre-screening data is then routed to BuildClinical's Secure Socket Layer (SSL) software, which encrypts all information to keep it private and HIPAA compliant. Their backend servers are stored in secure data centers in the USA.

Interested individuals will have the option of (a) completing the screening survey online, either via Qualtrics or BuildClinical, or (b) calling project staff to learn more about the study. In CBT-I trials with Veterans, attrition rates have ranged from 19 to 38% (Edinger et al., 2009; Germain et al., 2014; Karlin, Trockel, Spira, Taylor, & Manber, 2015). Estimating an attrition rate of 35%, we will recruit 68 participants over 34 months to obtain a final sample of **44 participants**. Approximately 9% of Veterans are women and 12-15% have PTSD; therefore, randomization will be stratified by gender and PTSD.

Screening. Individuals who are interested in the study will complete a brief eligibility screen online from remote locations and provide their first name, phone number, and email.

A research assistant will contact those who provide this information to explain the study in more detail and, if they are still interested, schedule them for the baseline assessment. Interested individuals whose only barrier to participation is travel/in-person appointments will be scheduled for a remote baseline visit.

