Penn Alcohol Craving Scale. The Penn Alcohol Craving Scale is a 5-item measure of alcohol craving in the past week. Participants rate the intensity, frequency, and duration of cravings, as well as their ability to resist acting on those cravings and their overall “average alcohol craving” for the past week. This measure has demonstrated good internal consistency and construct validity (Flannery, Volpicelli, & Pettinati, 1999).

8. Study Statistics

Power analysis. We chose to utilize G-Power, rather than a power analysis specific to multilevel modeling (MLM, sometimes referred to as mixed modeling) because powering for ANOVA will ensure we are adequately powered for MLM analyses, which will increase power to detect significant effects. Based on previous studies, the expected effect size is large for insomnia outcomes (based on trials with Veterans) (Germain et al., 2014; Talbot et al., 2014), medium for alcohol use outcomes (based on trials with college students) (Fucito et al., 2017), and medium for executive functioning outcomes (based on trials with fibromyalgia patients) (Miro et al., 2011). We used G-Power to determine the sample size needed for an a priori repeated measures ANOVA, within-between interaction ($\alpha = .05$, power = .95, groups = 2, repetitions = 4, correlation = .40). Based on these calculations, the sample size required to detect a small effect ($f = .10$) is 260; a medium effect ($f = .25$) is 44; and a large effect ($f = .40$) is 18. Assuming 2/month recruitment and 35% attrition, we plan to recruit 68

participants over 34 months to obtain a final sample of 44 participants. This will provide us with an adequate sample size to detect moderate to large group by time interactions.

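### Full maximum likelihood with no small-sample degrees of freedom makes tests of condition slightly too liberal at 44 participants; REML with Kenward-Roger or Satterthwaite degrees of freedom corrects this cheaply

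*Combined protocol and SAP*

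**What the plan says.** The treatment analysis in section 8, Study Statistics (Data analysis), is a two-level model with time at Level 1. The plan states that "Level 2 portions of the model will include the effect of condition and necessary covariates", and that the effect on insomnia is "tested by regressing condition on the Level 1 intercept and time effect". The estimator appears in the sentence on incomplete data: "missing values will be handled in MLM using full maximum likelihood estimation". Neither REML nor a small-sample degrees-of-freedom method is mentioned. The random-effects or covariance structure and the reference distribution for tests are also left open.

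The sample size in the same section comes from a repeated-measures ANOVA ("groups = 2, repetitions = 4, correlation = .40", alpha .05, power .95), for which the number needed for "a medium effect ($f = .25$) is 44". Section 4 (Recruitment) gives the recruitment target: "Estimating an attrition rate of 35%, we will recruit 68 participants over 34 months to obtain a final sample of" 44. The opening of section 4 instead says "Forty-four Veterans will be randomized to receive sleep hygiene" or CBT-I, and the Abstract gives 22 per arm.

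**The concern.** Full ML estimates variance components as though the fixed effects were known. It makes no allowance for the degrees of freedom spent on the condition means and covariates, so standard errors are biased downward in small samples. REML removes most of this bias, and Kenward-Roger or Satterthwaite degrees of freedom also allow for the variances being estimated. A plan that names full ML and is silent on degrees of freedom has neither protection unless the software supplies part of it by default.

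At stake are confidence intervals from these models that are slightly too narrow and a false-positive rate slightly above 5%. There is also a mild mismatch with the power analysis. The ANOVA F test that justifies 44 has finite denominator degrees of freedom and holds its alpha under its assumptions, whereas ML with a large-sample reference does not. Part of any apparent power gain from the multilevel model could therefore be excess type I error.

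**Working it through.** **Inputs from the protocol.** Alpha .05, power .95, 2 groups, 4 repetitions, correlation .40, f = .10, .25 and .40 (section 8, Power analysis); 35% attrition, 68 recruited, 44 final (sections 4 and 8); 22 per arm (Abstract). The reference distribution and covariance structure are not given, so both are varied below.

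**1. The plan's own figure.** Noncentral F with λ = N·f²·m/(1−ρ), df₁ = 3, df₂ = 3(N−2). For f = .25 and N = 44, λ = 44 × .0625 × 4/.60 = 18.33, df₂ = 126 and power is .957. The stated 260, 44 and 18 are all reproduced (power .951, .957, .956). 44/(1−.35) = 67.7, rounded up to 68, also matches.

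**2. Size of the bias (complete 1:1 data, condition only).** For a between-person effect, or condition-by-time with a random slope, ML SE / REML SE = √((N−2)/N).
- N = 44: √(42/44) = .977, so the SE is 2.3% too small.
- N = 68: √(66/68) = .985.

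**3. Type I error of a single contrast.** P = 2·Pr(t with N−2 df > c·√((N−2)/N)).
- N = 44, normal reference: 1.960 × .977 = 1.915, giving 6.2%.
- N = 44, t reference with 42 df: 2.018 × .977 = 1.972, giving 5.5%.
- N = 44, REML with a normal reference: 5.7%; REML with t: 5.0%.
- N = 68, normal reference: 1.960 × .985 = 1.931, giving 5.8%.

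The normal reference thus contributes about as much as ML itself.

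**4. Random intercept only, linear time.** Condition-by-time is then tested against within-person residuals with about 3N−2 = 130 df. The SE ratio is √(130/132) = .992 (0.8% too small), and type I error with a normal reference is 5.4%.

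**5. Omnibus 3-df Wald chi-square, N = 44.** Compound symmetry gives 6.4%. With unstructured covariance, the ML Wald statistic is T²·N/(N−2), and T²(N−4)/[3(N−2)] follows F(3, N−4). The critical value becomes 7.815 × 42/44 × 40/126 = 2.37 on F(3, 40), giving 8.5%. Keeping the chi-square reference under REML still gives 7.5%.

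**6. Covariates, N = 44.** The plan adds covariates conditionally and does not say how many; three is an illustration. For a between-person effect the ratio is √(39/44) = .941, giving 7.3% (normal) or 6.4% (t). For condition-by-time with a random slope (simulated, 20,000 complete-data trials, ML with a normal reference), type I error was 6.1% with no covariates, 6.6% with three on the intercept only, and 7.3% with three on intercept and slope.

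**7. Dropout.** Simulation, 4,000 trials per scenario (Monte Carlo SE about 0.35-0.4 points). Assumptions not in the documents: normal data; equally spaced times; for the slope model, intercept SD 0.6, slope SD 0.25 and residual SD 0.75; for the unstructured model, data with correlation .40; dropout depending on the last observed value.

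| Start N, model | Loss | SE ratio ML/REML | ML, normal | REML, Satterthwaite |
|---|---|---|---|---|
| 44, random slope | 0 | .977 | 6.4% | 5.3% |
| 44, random slope | 35% | .971 | 6.5% | 5.0% |
| 44, unstructured | 0 | .977 | 6.4% | 5.0% |
| 44, unstructured | 35% | .967 | 6.8% | 5.2% |
| 68, random slope | 35% | .981 | 6.7% | 5.7% |
| 68, unstructured | 35% | .979 | 6.7% | 5.7% |

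Point estimates were nearly identical under the two estimators. Kenward-Roger was not simulated.

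**8. Price of the change, N = 44.** With complete data the interval ratio is 2.018/(1.960 × .977) = 1.054. With 35% dropout it was 1.068 (slope) and 1.076 (unstructured). Rejection under a real effect fell by about 2.5 to 4 points, for example from 82.1% to 78.6%.

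**The case against.** The strongest reply is that the effect is small and depends on choices the plan leaves open. The sentence on ML concerns missing data, for which ML is valid under missing at random. No normal reference is planned, and with t the excess at 44 is half a point. With only a random intercept it is about 0.4 points even with a normal reference. The .05 appears in the power calculation, not as an analysis threshold, and the between-group effect sizes and their intervals are not said to come from the ML model. This is a pilot: recruitment, retention and satisfaction are untouched, and the alcohol and mediator analyses are described as exploratory and underpowered for smaller effects. All of this stands, and it limits the importance of the point. It does not make full ML the better estimator, because REML handles the missing outcomes on the same assumption. The insomnia test is also not labelled exploratory.

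A reader might infer more than the documents support:
- **That the analysis rests on about 28 participants** (44 less 35%). Sections 4 and 8 make 44 the number after attrition. If 44 are randomized instead, a likelihood analysis still uses the dropouts' earlier data. Up to 68 could contribute.
- **That every covariate worsens the treatment test.** For condition-by-time, growth at the full rate requires covariates in the slope equation too, which the plan does not specify. Baseline covariates enter only if related to both group and outcome, and predictors of attrition only when needed.
- **That every condition effect is affected equally.** The random-intercept case shows otherwise.
- **That the change is free.** It needs no participants or data, but intervals widen and the rejection rate falls.

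**Conclusion.** The point holds at modest size. At the planned 44, full ML understates the standard error of a between-person condition effect, or of condition-by-time with a random slope, by about 2-3%. Type I error is about 5.5% with a t reference and 6.2-6.8% with a normal reference, the upper end being with 35% dropout. With a normal reference and complete data it is about 5.8% at 68, and about 5.4% at 44 with a random intercept only. It exceeds the main range if covariates also enter the slope equation, and reaches about 8.5% for an omnibus chi-square test with unstructured covariance.

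These figures rest on normal outcomes, equal allocation and, for the dropout results, the assumed variance components and dropout mechanism. Which one applies depends on the covariance structure, the reference distribution and the number contributing data, none of which the plan settles. The bias is unlikely to change a conclusion, but the better method is readily available.

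**What to change.** In section 8, Study Statistics (Data analysis), replace full ML with wording such as: *Multilevel models will be fitted by restricted maximum likelihood, using all available outcome data under the missing-at-random assumption. Tests and 95% confidence intervals for condition effects will use Kenward-Roger (or Satterthwaite) degrees of freedom. Maximum likelihood will be used only for likelihood-ratio comparisons of models with different fixed effects.* Add one sentence stating the random-effects or covariance structure and whether covariates enter the intercept only or also the slope. The degrees-of-freedom method matters as much as REML, so both should be named.

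The cost is a software option and a few sentences. The small downside is the wider intervals and lower rejection rate in step 8, mostly the surrender of excess type I error. The sample-size calculation does not change.
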